1.6 Blinding

The study is conducted in a blinded manner. All subjects, investigators, their clinical staff, the clinical coordinating center, the data management group, and the sponsor staff and delegates will be blinded to the randomization codes. The local laboratories will also be blinded.

The IDMC reports and analyses for Closed Sessions will be organized by treatment arm (“unblinded”). In order to ensure confidentiality and minimize bias, the information will be provided to the IDMC by a group that is independent of the sponsor and blinded project team implementing the trial. A firewall will be maintained between the IDMC (unblinded) and the project staff (blinded). The IDMC will review safety data throughout the trial on an ongoing basis, and other data as requested by the IDMC, in addition to the interim analysis results.

The person responsible for the study drug labelling will be unblinded, as will the independent statistical group preparing the reports for the IDMC. The person responsible for the data management group, who manages the programming of the randomization system will be unblinded. This individual will be the contact person in the event that unblinding is necessary. This individual will not participate in data management and will only communicate unblinded data as set out below when contacted by the medical monitor.

Otherwise, randomization data will be kept strictly confidential, accessible only to authorized persons, until the time of unblinding after data lock at the time of interim analysis and at end of the study.

In case of emergency, a rapid unblinding procedure is available to investigators. If the investigator decides that the treatment code needs to be broken in the interest of subject safety, the investigator will have direct access to the ESCAPE-NA1 CRU center to request unblinding of the specific subject. The CRU will respond in writing to the investigator only with the unblinded patient treatment allocation.

Only the investigator requesting the unblinding will receive the unblinding information. The investigator will promptly inform the Sponsor when a request to unblind is made and the circumstances involved. Any case that is unblinded in this way will be documented in a blinded manner in central files.

1.7 Definitions

Baseline: A subject's baseline value for a given endpoint or parameter is defined as his/her latest measurement taken prior to study drug administration.

Prior and Concomitant Medications: Prior medications are defined as those taken within three days of treatment initiation. Concomitant medications are defined as those taken during study drug administration or after study drug has been administered through and including the Day 30 visit. All prior and all concomitant medications will be recorded on the electronic case report form (e-CRF).

Randomization: The time of randomization is defined as the time randomization occurred on the central server and this time is considered time zero for the study. All time windows are calculated from the time of randomization.

Treatment-Emergent Adverse Event: A treatment-emergent adverse event (TEAE) is one that first occurs or worsens in severity or frequency after study drug has been administered through to and including the Day 30 visit. SAEs are collected through the last study visit. Those AEs that start at the same time and date as the study drug administration and those that first occur or worsen after the start of study drug administration will be considered TEAEs.

AEs with partial or missing dates will be handled as follows:

- If the start day and/or month of the AE is missing and the AE in question occurs concurrently or subsequent to the study drug administration, the AE will be considered treatment-emergent.
- If the start date is completely missing then the AE will be considered treatment-emergent.

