6.1.4 Safety Outcomes of Special Interest

The primary safety outcomes are the frequencies of SAEs and 90-day mortality.

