8.1 Adverse Events

Additional analyses will consider the frequency of AEs and discontinuations due to AEs.

AEs will be collected until Day 30 and SAEs will be collected until Day 90 or the final contact. AEs will be summarized by presenting, for each treatment group, the number and percentage of subjects having at least one AE, having an AE in each body system and preferred term, by severity and relatedness to study medication. The frequencies and incidences of AEs occurring in subjects in the drug and placebo control groups will be summarized within treatment group by the Medical Dictionary for Regulatory Activities (MedDRA) System Organ Class (SOC). The frequencies and incidences of discontinuations due to AEs occurring in subjects in the NA-1 and placebo control groups will be summarized within treatment group.

If a given subject had more than one AE mapped to the same preferred term, then that subject will be counted only once within that preferred term.

When reporting TEAEs by maximum severity, if a given subject had more than one AE mapped to the same preferred term, then that AE will be counted once according to the maximal level of severity (Severe, Moderate, Mild).

When reporting TEAEs by relationship to study treatment, if a given subject had more than one AE mapped to the same preferred term, then that AE will be counted once according to the highest level of relatedness (Related, Probably, Possibly, Unrelated).

The following summaries (tables) of AEs and TEAEs will be provided by number (percentage) of subjects for each treatment group:

- All TEAEs by MedDRA preferred term

- All TEAEs by MedDRA SOC and by preferred term
- TEAEs (with a start date 0-30 days) by MedDRA SOC and by preferred term
- Serious TEAEs (with start date 0-90 days) by MedDRA SOC and by preferred term
- All TEAEs resulting in death by MedDRA SOC and by preferred term
- Event rate (%) for Serious TEAEs over the 90-day study period between NA-1 and placebo control subjects will be compared by a logistic regression model similar to that of the primary analysis.
- All TEAEs occurring in at least 5% of subjects in either treatment arm, by MedDRA SOC and by preferred term.
- All TEAEs by maximum severity (Severe, Moderate, Mild) by MedDRA SOC and by preferred term. Missing severity grades will be assumed as 'severe'.

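### The SAP's definition of a treatment-emergent event has two conflicting end dates; if the Day 30 one is programmed, later SAEs and fatal events leave the 90-day serious and fatal tables and the SAE regression

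*SAP*

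**What the plan says.** The treatment-emergent entry in SAP 1.7 makes three statements about time:

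- The opening statement admits events with onset or worsening "after study drug has been administered through to and including the Day 30 visit". It therefore closes the window at that visit.
- The next statement concerns collection only: "SAEs are collected through the last study visit". It does not say that later SAEs are treatment-emergent.
- The last statement, which also covers events beginning at the moment of dosing, ends: "those that first occur or worsen after the start of study drug administration will be considered TEAEs". No end date is given.

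SAP 8.1 repeats the collection rule: "AEs will be collected until Day 30 and SAEs will be collected until Day 90 or the final contact". Its list of by-arm outputs includes:

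- a serious-event table, "Serious TEAEs (with start date 0-90 days) by MedDRA SOC and by preferred term";
- the SAE comparison, specified as "Event rate (%) for Serious TEAEs over the 90-day study period between NA-1 and placebo control subjects", for which the method is logistic and modelled on the main efficacy analysis;
- a fatal-event table, "All TEAEs resulting in death by MedDRA SOC and by preferred term", for which no window is stated;
- all-TEAE, at-least-5%, severity and relationship tables, also with no window;
- a separate table of TEAEs starting on days 0 to 30.

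SAP 8.1 also lists all SAEs, all AEs leading to death and all deaths, without restricting them to treatment-emergent events.

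On the protocol side, section 6.1.4 states: "The primary safety outcomes are the frequencies of SAEs and 90-day mortality". Protocol 11.9.1 summarises SAEs over the 90-day period, including by severity and relatedness, and applies no treatment-emergent filter.

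**The concern.** One definition supports two different flags, and the choice decides whether an SAE starting on, say, Day 45 is counted. The outputs that depend on it matter. The regression of serious TEAEs is the SAP's only inferential comparison of SAE frequency, which is a primary safety outcome. The fatal-TEAE table is the SAP's only by-arm tabulation of fatal events by organ class and preferred term.

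Under the narrow flag, an output labelled 90 days would hold roughly 30 days of events, and the fatal table could show fewer events than the unfiltered fatal-AE listing in the same section. Under the open flag, tables headed as all TEAEs would mix non-serious events collected to Day 30 with serious events collected to Day 90 without saying so.

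SAP 8.5 assigns the IDMC reports to the independent statistical group and the final report to the Project Statistician's group. Two teams could read the definition differently and produce different counts from the same data.

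**Working it through.** The documents state no figure that depends on this definition. The check is therefore to follow one case through the outputs: an SAE, possibly fatal, with onset on Day 45.

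**Step 1. Do the 0-to-90-day labels rescue the event?** A table of serious TEAEs with start dates 0 to 90 selects records that satisfy both conditions:

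- flag closed at the Day 30 visit: {start of dosing to Day 30 visit} ∩ {days 0 to 90} = {start of dosing to Day 30 visit};
- open flag: {start of dosing onward} ∩ {days 0 to 90} = {start of dosing to Day 90}.

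A date filter cannot restore a record that the flag has already removed. The labels show what was intended but do not amend the definition.

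**Step 2. Outputs side by side for the Day 45 event.**

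| Output | Window stated | Flag closed at Day 30 visit | Open flag |
|---|---|---|---|
| Serious-TEAE table (SAP 8.1) | 0–90 days | out | in |
| Regression of serious TEAEs (SAP 8.1) | 90 days | out | in |
| Fatal-TEAE table (SAP 8.1) | none | out | in, if fatal |
| All-TEAE, severity and relationship tables (SAP 8.1) | none | out | in, beside non-serious events to Day 30 |
| 0–30 day TEAE table (SAP 8.1) | 0–30 days | out | out |
| Listings of SAEs, fatal AEs and deaths (SAP 8.1) | none | in | in |
| 90-day mortality (SAP 7.2.4; Protocol 11.9.2) | 90 days | in, if fatal | in, if fatal |

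Protocol 11.9.1 would count the event on either reading, because it uses SAEs and not TEAEs. The closed flag therefore departs from the protocol.

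**Step 3. Which reading fits the rest of SAP 8.1?** The separate 0-to-30-day table would be largely redundant if every TEAE already ended at the Day 30 visit. With the 0-to-90-day serious table, it points to the open reading as the intention. That intention contradicts the first sentence of the definition.

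**Step 4. Size.**

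- Follow-up time beyond the nominal cut-off: (90 − 30) / 90 = 60/90 = 67%. This is a share of days, not of events.
- The cut-off is a visit. The schedule allows Day 30 ± 5 days, so it falls between 30 − 5 = Day 25 and 30 + 5 = Day 35, depending on the subject.
- Subjects affected in the SAE regression: 1120 × (share with any SAE by Day 90) × (share of those whose first SAE starts after Day 30). The documents give neither share. As pure assumption, 20% and 10% give 1120 × 0.20 × 0.10 ≈ 22 subjects; 40% and 30% give 1120 × 0.40 × 0.30 ≈ 134, both arms together.
- Change in the 90-day mortality analyses: zero, because they count deaths and not TEAEs.
- Sample size and power: unaffected.

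**The case against.** The strongest reply is that the intention is clear enough. The serious table and the regression carry their own 90-day windows. The third sentence of the definition is open-ended. The 0-to-30-day table makes sense only if TEAEs in general run longer. A programmer following the output specifications would keep the late SAEs. The listings would show any that were missed, and 90-day mortality does not pass through the flag at all.

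Most of this stands, and it limits the point. A reader might infer that late SAEs and deaths disappear from the 90-day primary safety outcomes. The documents do not support that: mortality is untouched, and loss of SAEs follows only if the first sentence is programmed. Nor is the 67% evidence that two thirds of events would go missing, since nothing is said about onset times.

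The reply also weakens an argument from reconciliation with the mortality model. SAP 7.2.4 uses the ITT population and counts missing outcomes as deaths, so the fatal-TEAE table need not match it even with a 90-day window. The relevant comparison is with the fatal-AE listing and with observed deaths among treated subjects, since Protocol 10.1 has every death to Day 90 reported as an SAE.

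What the reply does not remove is the contradiction itself. The fatal table has no window to fall back on, listings are not by-arm summaries, and the open reading leaves the combined tables unlabelled.

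**Conclusion.** The point holds as an internal contradiction with a programming risk. SAP 1.7 conflicts with itself and with the 90-day outputs in SAP 8.1. If its first sentence is used as the flag, SAEs and fatal events starting after the Day 30 visit are lost from the by-arm serious and fatal tables and from the SAE regression, contrary to Protocol 11.9.1. The most exposed output is the fatal-TEAE table.

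No loss of events is shown, and the number at risk cannot be derived; the range of 22 to 134 subjects rests wholly on assumed rates. The conclusion needs only the wording of the two SAP sections. It should be settled before database lock, because the choice of flag should not be made with unblinded counts in view.

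**What to change.** In SAP 1.7, replace the single definition with two windows, both running from the start of infusion:

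- non-serious TEAE: onset or worsening through the Day 30 visit;
- serious or fatal TEAE: onset or worsening through Day 90 or final contact.

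In SAP 8.1:

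- add the 0-to-90-day window to the fatal table;
- confirm that the serious table and the SAE regression use the serious-event window;
- present SAEs by severity and by relatedness over 0 to 90 days, as Protocol 11.9.1 requires;
- label any all-TEAE table that combines non-serious events to Day 30 with serious events to Day 90.

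The severity and relationship reporting of SAEs should not be cut to 0 to 30 days. In the SAP's list of tables, those two attributes appear only in the all-TEAE tables, so such a cut would itself remove late SAEs from them.

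The cost is SAP wording, one additional flag in the AE dataset and the SAE tables by severity and relatedness. No new data are needed, because SAEs are already collected to Day 90. Both statistical groups should work from the same revised definition.

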2.0 ANALYSIS POPULATIONS

2.1 Intent-to-Treat Population

The primary efficacy analysis will be conducted on the ITT population, defined as all subjects randomized into the trial with grouping by randomized treatment, regardless of treatment actually received. Deceased subjects will be included in the ITT population with a mRS score of 6, NIHSS of 42 and Barthel Index of 0. An ITT analysis will also be conducted for the secondary endpoints, with subjects grouped according to the randomized (intended) treatment.

2.2 Safety Population

The safety population comprises all subjects receiving any amount of study drug. In safety analyses, subjects will be grouped according to treatment actually received.

2.3 Per Protocol Population

The primary analysis will be repeated on the Per Protocol (PP) population, defined to be all subjects randomized and treated, with no major protocol deviations. We define “major protocol deviations” as those with the potential to bias, confound, or otherwise obscure the treatment effect estimates or which involve ethical standards. This population will be determined via a blinded review of protocol deviations at the end of the trial before database lock and unblinding.

Missing data due to death during the study will not exclude a patient from the PP population (i.e. death is not considered a major protocol violation).

Prior to unblinding, the imaging from each subject at the time of inclusion will be adjudicated to determine whether they have met the criteria for endovascular intervention, and hence for the trial. This will include review of baseline NCCT, CTA and if performed CTP or MRP. Subjects who do not meet the imaging criteria outlined in the trial inclusion/exclusion criteria will be reviewed in a blinded fashion as described above to determine if they meet the criteria for a “major protocol deviation”..

3.0 INTERIM EFFICACY ANALYSES

An efficacy interim analysis after approximately 600 subjects complete the Day 90 follow-up (~56% information) will be conducted by the unblinded statistician in the independent Statistical Group (ISG) using the alpha spending function method^[11] with O'Brien and Fleming^[12] type stopping boundary for efficacy and a non-binding conditional power boundary (based on the observed trend at the interim analysis) for futility. Overwhelming efficacy at the interim analysis would occur if the test statistic crosses the O-F superiority boundary. For an interim analysis conducted at exactly 55.8% information, the superiority critical p-value for stopping (boundary value) would be 0.003 and that at the end of the study (primary analysis) would be 0.024, 1-sided. Conversely if the conditional power estimate based on the observed trend at the interim is <1% the trial may be deemed to be futile, contingent on consideration of other safety and efficacy factors (i.e., the futility boundary is nonbinding).

The IDMC may recommend stopping for futility at the interim analysis if the test statistic crosses the O-F or conditional power boundary. However, notwithstanding the O-F superiority critical p-value of 0.003 for stopping (boundary value) at the interim analysis of the primary efficacy outcome, the IDMC will be instructed that it should not recommend to stop the trial for overwhelming efficacy unless otherwise instructed by the Steering Committee at the Open Session of the IDMC meeting. The IDMC Charter will provide further details on the rationale for, and how, these recommendations will be communicated.

To prevent operational bias all interim results on safety and efficacy will be reported only to the IDMC, keeping the sponsor, project team, investigators and subject blind to results by treatment assignment during the study. Firewalls will be in place at the Statistical Group preparing all interim reports to protect and sequester all interim results on safety and efficacy

4.0 DATA REVIEW

Relevant past medical history as well as prior and concomitant medications will be listed. AEs will be coded using the Medical Dictionary for Regulatory Activities (MedDRA) to assign a system organ class (SOC) and preferred term to each AE.

When the database has been declared complete and accurate, the database will be locked and subsequently unblinded.

5.0 MISSING DATA AND DATA TRANSFORMATION

5.1 Missing Data

Every effort will be made to keep missing data, particularly the Day 90 outcome assessments, to a minimum. However, some missing data may be inevitable due to, for example, loss to follow-up. This was kept to a minimum of 1.3% in the ESCAPE trial.^[2] Deceased subjects will be assigned scores of 6 on the mRS, 42 on the NIHSS, 0 on the Barthel Index and be counted as non-responders. For the primary analysis for regulatory submission, we will assume that subjects who are missing the primary endpoint data will be considered non-responders. If more than 5% of subject randomized are missing the primary endpoint, two sensitivity analyses will be employed to examine alternatives to this extreme single-value imputation: (1) multiple imputation of the ordinal mRS score which will then be converted to the corresponding binary score; and (2) if, as expected, $\leq 5\%$ of the mRS data are missing, a completers' analysis.

5.2 Data Transformation

No transformation of the data is planned other than for volume of stroke. Note that stroke volume data are often dispersed and highly non-normal and can be normalized with an inverse cubic root transformation. Alternate Box-Cox power transformations may be required, depending upon the data distribution (note: the inverse cubic root transformation is a member of the Box-Cox power series). No data transformation is planned for the primary analysis.

6.0 STATISTICAL METHODS

The software used for all summary statistical analyses will be SAS® (SAS Institute, Inc.) version 9.4 or later.

Unless otherwise noted, categorical data will be summarized for each treatment group using counts and percentages, with the denominator for percentages being the number of subjects in the population of interest. Unless otherwise noted, continuous data will be summarized for each treatment group using the number of observations (n), mean, standard deviation (SD), median, minimum, and maximum. Some continuous data will be reported as the median, interquartile range (IQR), minimum and maximum according to the clinical meaning of the data.

Percentages will be rounded to one decimal place, except 0% and 100% will be displayed without any decimal places. Minima and maxima will be rounded to the precision of the original value; means and medians will be rounded to one decimal place greater than the precision of the original value; SDs will be rounded to two decimal places greater than the precision of the original value. P-values will be reported to four decimal places (0.xxxx), with values less than 0.0001 presented as <0.0001.

Inferential analyses will generally include statistics such as 2-sided 95% confidence intervals (CI), and p-values. Unless stated otherwise, all statistical tests will be 2-sided hypothesis tests performed at the 0.05 level of significance.

In order to protect the overall trial false positive rate, the primary efficacy analysis, key secondary outcome analysis and secondary endpoints will be analyzed in a fixed sequence, stopping and calling all subsequent analyses exploratory (and accepting the null hypothesis) at the first failed hypothesis test in the sequence. The fixed sequential order is:

1. Primary efficacy outcome
2. Key secondary outcome analysis (shift analysis using proportional odds model);
3. Secondary efficacy endpoints, as specified in the order presented below in Section 6.7.

All data will be included in subject data listings for all randomized subjects.

A final, unblinded, statistical report that will include both efficacy and safety evaluations will be generated upon completion of the trial. The final report will be distributed to the Trial Steering Committee

6.1 Subject Disposition

Subject disposition will be summarized and tabulated for ITT, PP and Safety populations. The summaries will include the number and percentage of subjects that completed the study and those that terminated early from the study (i.e., left the study prior to the Day 90 visit). Early terminations will be categorized by the reason for study discontinuation. Death will not be considered early termination.

In addition, a tabulation of the number and percentage of subjects randomized will be summarized by site for the ITT population.

6.2 Protocol Deviations and Protocol Violations

The case report form pre-specifies the major protocol violations and protocol deviations. The data will be reviewed regularly to identify both. Major protocol deviations will be determined during a data review meeting prior to database lock. These may include but may not be limited to:

- Enrollment did not comply with inclusion criteria
- Enrollment did not comply with exclusion criteria
- Consent not obtained.
- Subjects who did not receive a per-protocol dose (none or incomplete dose), or received an incorrect study drug vial, or received the study drug infusion over 15 or more minutes.

The number and percentage of subjects in the ITT population with protocol violations will be summarized by treatment group and overall.

